Hypothesis 3: Participants receiving cooking support will have lower scores on a measure of perceived stress than participants who do not receive cooking support. This will be true at all measurement time points.

Aim 4: To explore the reasons why students cook or do not cook.

Hypothesis 4: There will be common themes defining why student choose to cook or not cook at home.

Study Design: Describe the research design, including a description of any new methodology and its advantage over existing methodologies.

We propose a randomized trial to evaluate whether cooking classes produce greater gains in cooking skills and food agency compared to a control condition, as well as whether provision of meal delivery and recipes result in more frequent cooking than no meal delivery or recipe provision. We will randomize 64 students to either the intervention condition where they will take part in six weeks of hands on cooking classes, or the control condition where they will receive no cooking instruction during the fall semester. Following the completion of cooking classes and the start of the spring semester, one active cooking (treatment) group and one control group will receive another 12 weeks of intervention while the other two groups will receive no further instruction. The two continued intervention groups will be subscribed to a meal delivery service for six weeks, and then receive only recipes for another six weeks. Assessments will be conducted at baseline and following each phase of the intervention for all groups.

Study Population

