Following signed consent participants will be asked to complete a few baseline tasks to be fully eligible for participation in the study. These tasks include three days of food tracking using ASA-24, baseline surveys, submission of cooking frequency and food photos, and finally a one-on-one interview with study staff to discuss their participation. These baseline tasks are intended to ensure participant compliance and retention during the 18-week intervention.

Eligible participants will be assigned to one of four scheduled class periods based on their stated availability or recruited for the control condition. Once all classes are full, a random assignment table will be used to determine the group assignment for each class period. Participants will then be informed of their group assignment (active with follow up or active no follow up). Participants who are in the control condition will be randomly assigned to either a group that receives follow-ups or a group that does not. Groups will not be stratified by any criteria, and instead will be determined based upon participant availability.

Surveys will be administered through the study REDCap website at baseline and study end. Participants will receive links to the questionnaires and reminders to complete questionnaires via email. These measures are outlined in greater detail below. In addition to questionnaires, weekly data collection (Photo Elicitation and Cooking Frequency) will be administered through REDCap. Participants will receive a weekly email with links to a REDCap data collection tool. Participants will receive reminders to complete weekly data submissions, and will be given information regarding a helpline for using the study website and data entry.

Table 1 outlines when each measure will occur during the study.

Measures	Baseline	Weekly	Phase 1	Phase 2	Phase 3
ASA24					
HEI (calculated)					
CAFPAS					
Cooking Perceptions and Behaviors					
PSS					
Intuitive Eating Scale					
Interoceptive Awareness					
Cooking Frequency					
Photo Elicitation					
Class Evaluation					
Meal Kit Evaluation				X	
COVID-19 Questionnaire					X

Quantitative Measures

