After the final cooking class, participants in groups B and D will receive no further instruction, though they will be asked to complete surveys and data collection through the remainder of the study phases. Phase 2 will begin in mid-January 2020. Participants in Groups A and C will receive weekly meal kit deliveries for 6 weeks. Meal kits will be delivered to students’ homes once per week and will include the ingredients and instructions for preparing 3 separate meals. Phase 3 will be immediately following phase 2. Participants in groups A and C will receive an email at the beginning of each week for the next six weeks that provides them with 5 healthy recipes developed by the study team. Students will generally receive the same recipes though; modifications may be made for participants with special dietary restrictions.

Facilities and Equipment Needed

Cooking Labs – The cooking classes and demonstrations will take place in the Nutrition and Food Sciences teaching kitchen located in the Marsh Life Science building. The teaching kitchen has room for 16 students to complete hands on cooking labs, and an additional space where students can get directions, eat, and watch cooking demos. The kitchens are fully stocked with the necessary kitchen equipment.

Follow-up Data Collection

Participants will be alerted by email to complete their follow-up assessment questionnaires which are anticipated to take approximately 30 minutes to complete and 3 days of the ASA24 (approximately 30 minutes per day).

All participants will be offered small incentives such as cooking equipment, cookbooks, gift cards, etc. (valued at approximately \$ 5-25) after completion of the follow-up data collection. Those in the Control Group will also receive a small incentive for completing their baseline measures.

For research involving survey, questionnaires, etc.: Describe the setting and the mode of administering the instrument and the provisions for maintaining privacy and confidentiality. Include the duration, intervals of administration, and overall length of participation. (describe and attach all instruments)

Not applicable

Questionnaires and ASA-24 logs will be administered at baseline and at the end of each study phase.

Photo elicitations and cooking frequency surveys will be administered weekly during the active study phases.

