Recruitment materials will ask participants to take part in a study on college students, cooking behavior, and health. Materials will list the study inclusion criteria, and explain that students will all receive incentives for completing study assessments. Recruitment materials for the intervention portion of the study will also explain that participants will have the opportunity to participate in a seven-week series of cooking classes, as well as a chance to receive free meal kits for 6-weeks.

Interested persons will be directed to a secure online recruitment application, which provides an outline of the study and queries for basic contact information, demographic information, and eligibility criteria. Individuals who appear likely to be eligible based on this online application will sign up for an in-person information session conducted by research staff during which the study will be reviewed in detail, questions will be addressed and an informed consent document will be provided to take home. After considering the study (participants will have a minimum of 1 week), interested participants will be asked to sign a consent form at the first baseline data collection visit. Consent forms will have been approved by the University of Vermont Institutional Review Board.

FINANCIAL CONSIDERATIONS

Expense to Subject: If the investigation involves the possibility of added expense to the subject (longer hospitalization, extra studies, etc.) indicate in detail how this will be handled. In cases where the FDA has authorized the drug or device company to charge the patient for the experimental drug or device, **a copy of the authorization letter from the FDA or sponsor must accompany the application. Final approval will not be granted until the IRB receives this documentation.**

There are very limited circumstances under which study participants may be responsible (either directly or via their insurance) for covering some study-related expenses. If the study participant or their insurer(s) will be billed for any portion of the research study, provide a justification as to why this is appropriate and acceptable. For example, if the study involves treatment that is documented standard of care and not investigational, state so. In these cases, the protocol and the consent should clearly define what is standard of care and what is research.

No expenses are anticipated for participants.

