At the conclusion of recruitment for the Cooking Class Condition, those who completed the initial application, but did not go farther in the recruitment process will be asked if they would like to participate in the control arm of the study. To participate, they will be asked to attend an Office Hours appt. with the PI or Study Coordinator to fill out informed consent and then will be given access to the baseline data collection online. Those in the Control Condition will also then be randomized to either receive meal kits and recipes in Phases 2 and 3 of the study, or to receive no further support. The contact information and screening information of participants who decline consent will be destroyed.

Information Withheld From Subjects: Will any information about the research purpose and design be withheld from potential or participating subjects? If so, explain and justify the non-disclosure and describe plans for post-study debriefing.

Not applicable

Attach full grant application, including budget information and/or any contract or draft

All materials must be submitted electronically to the IRB via InfoEd. Proper security access is needed to make electronic submissions. Visit the [InfoEd Resource Materials](#) page for more information.

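### Follow-up support is drawn, and for class students disclosed, before Phase 1, about 11–16 weeks before the first kit; anticipation and unequal early loss could bias support versus none

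*Combined protocol and SAP*

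**What the plan says.** **Class students (Groups A and B).** Under Procedures, eligible students are placed in one of four class periods according to availability. Then: "Once all classes are full, a random assignment table will be used to determine the group assignment for each class period". Next: "Participants will then be informed of their group assignment (active with follow up or active no follow up". The Inclusion/Exclusion Criteria require baseline measures to be finished before the first class.

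**Controls (Groups C and D).** Under Informed Consent, Control Condition, controls are approached after class recruitment has closed: "those who completed the initial application, but did not go farther in the recruitment process will be asked if they would like to participate". They consent, get access to the online baseline, and "Those in the Control Condition will also then be randomized to either receive meal kits and recipes in Phases 2 and 3" of the study. Neither this section nor Procedures says when they learn the result.

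**Timing.** The Intervention section puts Phase 1 in October 2019 and states "Phase 2 will begin in mid-January 2020". A and B are treated alike in Phase 1, as are C and D. The pairs diverge only when kits start.

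**Inducement.** Under Recruitment, materials for the intervention portion offer cooking classes "as well as a chance to receive free meal kits for 6-weeks".

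**Analysis.** Under Statistical Considerations, Aim 2 uses repeated measures ANOVA between groups and, within subjects, from the end of the fall semester to the end of each support period. The plan gives no analysis set, missing-data method or drop-out allowance.

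**What is randomised.** Study Design says "We will randomize 64 students to either the intervention condition where they will take part in six weeks of hands on cooking classes" or to control, and the opening summary says all 64 are randomised to the four conditions. Procedures and the Control Condition text describe a random draw only for follow-up support.

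**The concern.** An allocation that has no effect until January has no reason to exist, or to be known, in October. Once it is known, two things can happen before any kit arrives.

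First, students may behave or report differently in Phase 1. Cooking frequency is self-reported each week, and the kits are a benefit that class recruits were told they might receive. The end-of-fall value, which Aim 2 treats as the starting point for maintenance, could then already be affected by allocation.

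Second, students who know they will get nothing further may leave sooner, during Phase 1 or the winter break. That loss comes after the draw and may depend on it, so the groups entering Phase 2 need not be comparable.

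At stake is the part of Hypothesis 2a that compares support with no support. Under the operational text, this is the only comparison protected by a random draw.

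**Working it through.** **1. The plan's own figure.** 4 groups × 16 = 64, as stated. It is a kitchen-capacity figure with no power calculation behind it. Support versus none is A+C (32) against B+D (32).

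**2. Sequence for class students.** Baseline complete → classes full → draw per period → participants told → first class. That disclosure precedes Phase 1 is inferred from this order; no date is stated.

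**3. Lead time.** Phase 1 start: 1–31 October 2019, reading the October statement as the start. First kit: 13–20 January 2020, an assumed reading of mid-January.

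| First class | First kit | Days | Weeks |
|---|---|---|---|
| 1 Oct | 20 Jan | 111 | 15.9 |
| 1 Oct | 13 Jan | 104 | 14.9 |
| 31 Oct | 20 Jan | 81 | 11.6 |
| 31 Oct | 13 Jan | 74 | 10.6 |

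Disclosure comes before the first class, so for any given start date these are minimum leads. If disclosure waited until six weekly classes were over, the lead would be at most (74 − 42)/7 = 4.6 to (111 − 42)/7 = 9.9 weeks. None of it would fall inside Phase 1.

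**4. Selective early loss (all inputs assumed).** If the least motivated fraction p leaves, mean motivation among those remaining rises by φ(z_p)/(1 − p) SD. Multiplying the difference between groups by the motivation–outcome correlation r gives the bias in outcome SD.

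| Loss, support vs none | Shifts (SD) | Difference | × r = 0.3–0.5 |
|---|---|---|---|
| 5% vs 15% | 0.109, 0.274 | 0.166 | 0.05–0.08 |
| 10% vs 25% | 0.195, 0.424 | 0.229 | 0.07–0.11 |
| 10% vs 35% | 0.195, 0.570 | 0.375 | 0.11–0.19 |

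The bias runs against support, because the no-support group keeps its more motivated members. The table applies the unequal loss to all of A+C and B+D, so it assumes that controls also know their allocation. If only A and B know, take 25% loss in B and 10% in A, C and D. The B+D shift is then (12 × 0.424 + 14.4 × 0.195)/26.4 = 0.299. The difference from A+C is 0.299 − 0.195 = 0.104, and the bias is 0.03–0.05 SD.

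**5. Anticipation (assumed).** Suppose knowing the allocation shifts the end-of-fall score by a SD between the support groups and does not carry over to later scores. Change from end of fall is then off by a in the opposite direction. The standard error for 32 versus 32 is √(2/32) = 0.25 SD, with change SD equal to 1 and no allowance for clustering. A true null is rejected at the two-sided 5% level with probability 6.9% for a = 0.1, 12.6% for a = 0.2 and 22.4% for a = 0.3. If only A and B know, a 0.2 SD shift between them averages to 0.1 SD over the full contrast, giving 6.9%.

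**6. Unit of the draw.** For classes the draw is per period: four periods as stated, or two if each holds 16 (32/16). So A versus B rests on very few randomised units, and each unit was filled by availability.

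**The case against.** The strongest reply is that much of this is conjecture. The documents give no drop-out rate, no difference in loss and no link between motivation and outcome. Assuming that exactly the least motivated leave is an extreme case. Even so, 0.07–0.11 SD is less than half the 0.25 SD standard error, in a pilot that claims no power. That stands: the size is illustrative only.

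The plan also works at retention, through baseline tasks, reminders, incentives for follow-up data, and continued data collection in B and D. Class students complete baseline before the draw. An as-assigned contrast anchored on that baseline, with complete follow-up, would validly estimate the effect of being told of and offered support. That also stands, and it confines the harm to change from end of fall, to use of Phase 1 values as covariates, and to unequal loss. But the Aim 2 text does not specify that analysis.

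A reader might infer that every student is told before Phase 1. The documents do not support this: the disclosure sentence covers only A and B, and for C and D the timing is unstated. The kit inducement is likewise documented only for the intervention recruitment materials.

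A reader might also take support versus none as the only randomised contrast. Procedures and the Control Condition text point that way, but the opening summary and Study Design say that all 64 are randomised to the conditions. The conflict has to be resolved, not assumed away.

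Finally, the document carries an approval stamp of 4/14/2020, after the planned start of kits. A change of draw date may no longer be possible for this cohort.

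**Conclusion.** The point holds as a design weakness with a cheap remedy, not as a demonstrated bias. For class students, draw and disclosure come before Phase 1 by sequence, at least 10.6–15.9 weeks before the first kit under the assumed dates. For controls, the draw is stated and the time of disclosure is not.

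Nothing in Phase 1 needs the allocation, and the Aim 2 within-subject reference lies after disclosure to class students. Anticipation and unequal early loss could therefore distort support versus none. The documents do not allow the size to be computed. The illustrative 0.07–0.11 SD rests on assumed losses of 10% and 25%, loss of the least motivated only, r = 0.3–0.5, and controls knowing their allocation. It falls to 0.03–0.05 SD if only A and B know.

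It would be too much to say that a later draw brings bias to zero. It removes, in expectation, the part due to loss before the draw. Loss during Phases 2 and 3 remains, and drawing very few class periods gives little assurance that the groups actually compared are balanced.

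**What to change.** - **Timing.** In Procedures and in Informed Consent, Control Condition, place the draw of follow-up support for class and control students after the end-of-Phase-1 assessments, among those still enrolled. If the table must exist earlier, keep it concealed until then. State when each group is told.
- **Consent.** Tell students that support will be decided by chance in January.
- **Unit.** State whether the draw is per student or per class period. Kits go to homes and recipes go by email, so a per-student draw is feasible.
- **Reconcile.** Make the opening summary and Study Design agree with Procedures and the Control Condition text on what is randomised.
- **If allocation has already been disclosed.** Analyse support versus none as assigned, with the pre-draw baseline rather than the end-of-fall value as reference. Confirm that each control's baseline was complete before the draw, since the text gives them access to it but does not say it was finished. Report loss by group before the first kit, and when controls were told. Use the later draw in the larger study that this pilot is meant to inform.

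Cost: amended procedures and consent text, with no extra visits or staff. The downside is that students wait until January to learn whether they receive kits.

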With the rise in obesity in America correlating strongly with the decline in the frequency that Americans cook at home, cooking may be an important behavior to encourage to promote health. Increasing the prevalence of Americans who cook meals at home may be an important health behavior to target, because cooking at home is widely regarded as being healthier than consuming food away from home. While interventions are limited in number and scope, the positive benefits of cooking at home on dietary quality seem to cut across age groups and populations from college students to older adults.^{6,7} Cooking classes may be an important intervention target because they may increase one’s food agency. Thinking of cooking as a health behavior, cooking classes may be equivalent to exercise classes for someone trying to increase their physical activity. The exercise classes give one the skills, social structure, and self-efficacy to begin exercising on one’s own. This study is designed to test whether cooking classes could do the same for someone’s food agency and cooking frequency.

The proposed pilot study is a trial to evaluate whether cooking classes produce greater gains in cooking skills and food agency compared to a control condition that does not receive cooking classes, as well as whether provision of meal delivery and recipes result in more frequent cooking than no meal delivery or recipes. There will be three phases to the study intervention and four study conditions. All conditions will receive 6 weeks of cooking classes, either active or demonstration, and two conditions will also receive a continued intervention including 6 weeks of meal kit delivery service followed by another 6 weeks of recipe provision.

Phase 1- Cooking classes or control condition. All participants in the cooking classes condition will attend 1 kitchen intensive session followed by 1 cooking class per week for 6 weeks. Control condition participants will receive no cooking instruction.

Phase 2- Meal Kits. Assigned participants will receive meal kit deliveries once per week for 6 weeks.

Phase 3- Recipes. Assigned participants will receive 5 healthy recipes by email once per week for 6 weeks.

We will randomize 64 students to one of four intervention conditions.

Group A (n=16) - Active cooking classes followed by meal kits and recipes

Group B (n=16) - Active cooking classes followed by no further instruction

Group C (n=16) – Control condition followed by meal kits and recipes

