Group D (n=16) – Control condition followed by no further instruction

Assessments will be conducted at baseline, and following each phase.

Aim 1: Aim 1: To pilot test a food-agency focused cooking class pedagogy to motivate college students to cook more frequently, improve their diet quality, and increase their sense of food agency.

Aim 2: To evaluate if providing students with six weeks of a meal delivery service and then six weeks of recipes after completion of cooking classes maintains gains in diet quality, cooking frequency, and food agency.

Aim 3: To positively influence participants' stress levels.

Aim 4: To explore the reasons why students cook or do not cook.

Cooking Classes: Those in the Cooking Classes Intervention groups will attend one cooking class per week for six weeks led by a trained chef and based on an established curriculum designed to increase one's food agency, or cooking confidence. Participants will cook one recipe per week as well as participant in various tastings.

Control Condition: Participants in the Control Condition will not attend weekly cooking classes. They will be instructed to cook or not cook as they usually do. They will be asked to complete baseline measures, as well as measures at the end of each intervention period.

Meal Kits: With the meal delivery service, participants will get all the ingredients they need to make a meal as well as a recipe for the meal which includes step-by-step photos. They are then responsible for doing the actual cooking of the meal. Students will all receive kits for 3 meals per week from the same delivery service and will have the option to select meals that fit their dietary needs (vegetarian, gluten free, etc.). Meal kits are designed to serve two individuals therefore students should have enough food for six meals, though they will only need to cook three times. The service used is open to the public, therefore students who enjoyed the meal kit service could opt to continue service and pay for it themselves. However, students will be instructed to wait until study completion to do so.

Recipes: Recipes will be designed by the research team, which includes three registered dietitians and a trained chef. Students will receive recipes for five healthy meals per week. Participants will need to shop, budget, and plan on their own. Recipes will accommodate major dietary preferences including vegetarian and gluten-free.

PURPOSE AND OBJECTIVES

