Cooking and Food Provisioning Action Scale (CAFPAS): The CAFPAS scale measures cooking and food preparation practices or the degree to which individuals can set and achieve cooking and food provisioning goals. The CAFPAS includes 28 items with three subscales: Food Self-Efficacy, Food Attitude, and Structure. The CAFPAS scale has been shown to predict reported meals cooked per week and has adequate internal validity and test-retest reliability.⁴³

Perceived Stress Scale (PSS) – The PSS is a reliable and valid measure of perceived stress in adults including college students.⁵⁹ It is composed of ten questions that assess how often one perceives various forms of stress such as feeling unable to control important events, being upset by something unexpected, and feeling nervous.⁵⁹ Every six weeks participants, during the study period, participants will fill out the PSS, so any impact of cooking practice on stress can be illuminated.

The Cooking Perceptions and Behaviors Questionnaire: The Cooking Perceptions and Behaviors questionnaire is a 53-item survey designed to assess three factors: Perceptions of Cooking, Cooking Confidence and Attitudes, and Cooking Behaviors. This survey has been used in previous research to measure cooking perceptions and behavior.⁴⁴

Intuitive Eating Scale-2: The Intuitive Eating Scale-2 is a 23-item survey designed to assess the degree to which someone is able to listen to hunger and fullness cues when they decide what, when, and how much to eat.⁴⁵ The scale is composed of four sub-scales, Unconditional Permission to Eat, Eating for Physical Rather Than Emotional Reasons, Reliance on Hunger and Satiety Cues, and Body-Food Choice Congruence. This survey has been used in previous research with college students.⁴⁵

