A repeated measures ANOVA analysis will be used to compare changes in intuitive eating, diet quality and food agency over time both within the groups and between the groups. A generalized linear mixed model design will be used to compare the frequency of cooking at home each week over time and between the groups.

Aim 2: To evaluate if providing students with six weeks of a meal delivery service and then six weeks of recipes after completion of cooking classes maintains gains in diet quality, cooking frequency, intuitive eating, and food agency.

Hypothesis 2a: Meal delivery service will better maintain cooking frequency, intuitive eating skills, food agency and diet quality versus recipe provision only. Both meal delivery service and recipe provision will result in more frequent cooking, higher food agency, and higher diet quality the provision of no cooking support.

Hypothesis 2b: During both meal delivery service provision and recipe provision, those in the Cooking Class Condition will maintain higher levels of food agency, cooking frequency, and diet quality than those in the Control Condition.

Repeated measures ANOVA analyses will be used to compare between subjects effects from the meal delivery and recipe only interventions, as well as to compare the material support interventions against the control group. Repeated measures ANOVA will also be used to compare within subjects effects from end of fall semester to the end of each six-week material support intervention.

Aim 3: To positively influence participants' stress levels.

Hypothesis 3: Participants receiving cooking support will have lower scores on a measure of perceived stress than participants who do not receive cooking support. This will be true at all measurement time points.

A repeated measures ANOVA will be used to determine differences both between groups and over time in scores of perceived stress.

Aim 4: To explore the reasons why students cook or do not cook.

Hypothesis 4: There will be common themes defining why student choose to cook or not cook at home.

This is an exploratory aim, and qualitative analysis will be used to deduce popular themes.

Sample Size

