This is a pilot study with no previous data available to calculate expected statistical power. The sample size chosen was practical as our foods lab can only accommodate 16 people at a time. One group of each intervention arm (four) would give us data on approximately 64 subjects. This preliminary data will be used to determine the sample size power needed for a larger study with sufficient statistical power.

Inclusion/Exclusion Criteria: Eligibility and ineligibility criteria should be specific. Describe how eligibility will be determined and by whom. Changes to the eligibility criteria at a later phase of the research have the potential to invalidate the research.

Interested individuals will be directed to a study application that provides details about the study program and asks a series of screening questions. These questions are intended to determine basic eligibility for the study. Ineligible applicants will be notified of their ineligibility and directed to other campus resources related to cooking and meal planning. Eligible applicants will be directed to sign up for an in-person information session.

Inclusion criteria:

- Student at the University of Vermont
- Age 18-25
- Cooks dinner at home no more than 3x/week
- Access to a kitchen at home
- Lives independently off campus (may have roommates but may not live with guardians)
- Availability during scheduled cooking classes/demonstrations

Individuals will be excluded from the study if they do not complete baseline data collection measures prior to the first class meeting. Baseline data measures include four questionnaires (PSS, CAFPAS, Cooking Behavior, and intuitive eating scale), three days of ASA-24 logs, one photo elicitation survey, and one cooking frequency survey.

Inclusion of Minorities and Women: Describe efforts to include minorities and women. If either minorities or women are excluded, include a justification for the exclusion.

Women and minorities will be included. During recruitment, we will work with UVM Office of Student and Community Relations to ensure that our recruitment materials and procedures capture eligible students of all demographics.

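### The 32 controls are drawn 16 versus 16 to support or no support with no stratification and no planned baseline adjustment, so a baseline gap above 0.5 SD on any one measure arises by chance about one time in six

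*Combined protocol and SAP*

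**What the plan says.** All references are to the Combined protocol and SAP.

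- **Group sizes (design summary).** "Group C (n=16) – Control condition followed by meal kits and recipes" and "Group D (n=16) – Control condition followed by no further instruction".
- **Assignment (Procedures, after the Recruitment paragraph).** Active students are placed in class periods by availability, and whole periods are then randomised. For controls: "Participants who are in the control condition will be randomly assigned to either a group that receives follow-ups or a group that does not". The next sentence covers all groups: "Groups will not be stratified by any criteria, and instead will be determined based upon participant availability".
- **Timing (Informed Consent, Control Condition).** Controls consent, are given access to the online baseline, and: "Those in the Control Condition will also then be randomized to either receive meal kits and recipes in Phases 2 and 3 of the study".
- **Baseline completion (Inclusion/Exclusion Criteria).** "Individuals will be excluded from the study if they do not complete baseline data collection measures prior to the first class meeting". The listed measures include CAFPAS, the cooking-frequency survey and three ASA-24 days.
- **CAFPAS (Quantitative Measures).** "The CAFPAS scale has been shown to predict reported meals cooked per week and has adequate internal validity and test-retest reliability".
- **Analysis (Statistical Considerations, Aim 2).** Repeated measures ANOVA is to "compare the material support interventions against the control group", and also to assess within-subject effects from the end of fall to the end of each support phase. No covariate is named.

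**The concern.** C versus D is the only contrast in which single students are randomised. In the active arm whole class periods are drawn, and controls are recruited from applicants who went no further in recruitment for the classes. The control draw therefore gives the cleanest evidence on support versus no support.

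The sentence that rules out stratification also says that availability determines the groups. For controls that contradicts the sentence before it, and class availability has nothing to decide for people who attend no class.

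With 16 per group, a sizeable chance gap on a main outcome is not rare, and the plan handles it neither in the draw nor in the model. An unlucky gap would leave the support estimate hard to read. The Sample Size section says these data will be used to size a larger study, so that uncertainty carries forward.

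**Working it through.** **Plan's own figure.** 4 groups × 16 = 64, as stated. The size was set by kitchen capacity. There is no power calculation to reproduce.

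**Inputs.** 16 per group (design summary). Everything is in baseline SD units, so no outcome SD is needed. The correlations are assumptions, shown over 0.3 to 0.7, and measures are taken as normal.

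**1. Chance gap as planned.**
- SD of the difference in baseline means = √(1/16 + 1/16) = √0.125 = 0.354.
- P(|gap| > 0.5) = 2 × (1 − Φ(0.5/0.354)) = 2 × (1 − Φ(1.414)) = 0.157, or 1 in 6.4.
- Using the pooled sample SD (t, 30 df) gives 0.168. Coin-flip group sizes give 0.164. With 14 or 12 per group it is 0.186 or 0.221.

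**2. Gap after a median split with 8:8 in each half (simulation, 100,000 draws).**
- On the stratifying measure, the SD of the gap is 0.216 (variance 0.0467) and P(|gap| > 0.5) is about 2%.
- On another measure correlated r with the stratifier, gap variance = r² × 0.0467 + (1 − r²) × 0.125:

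| r (assumed) | Variance | SD | P(gap > 0.5 SD) |
|---|---|---|---|
| 0.3 | 0.1180 | 0.343 | about 14.5% |
| 0.5 | 0.1054 | 0.325 | about 12% |
| 0.7 | 0.0866 | 0.294 | about 9% |

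**3. Effect of a gap on the support estimate.** With pre-post correlation ρ, a baseline gap g moves a post-level contrast by ρg and a change-from-baseline contrast by −(1 − ρ)g. At ρ = 0.5 and g = 0.5, each is 0.25 SD in size.

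**4. Precision gained for CAFPAS by stratifying on CAFPAS.**
- Post level: variance goes from 0.125 to ρ² × 0.0467 + (1 − ρ²) × 0.125.
- Change from baseline: variance goes from 2(1 − ρ) × 0.125 to (1 − ρ)² × 0.0467 + (1 − ρ²) × 0.125.
- At ρ = 0.5 both go from 0.125 to 0.25 × 0.0467 + 0.75 × 0.125 = 0.1054, so the SD falls from 0.354 to 0.325, about 16% less variance. Simulation gave 0.322 to 0.326, that is, 15–17%.

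**5. Change from end of fall.** If baseline CAFPAS is equally correlated with the end-of-fall and post-support values, its contribution cancels in the difference, so balancing it gains nothing. Simulation at correlation 0.5 agrees: 0.354 SD unstratified, 0.352 SD stratified. With correlations of 0.7 for adjacent and 0.5 for distant visits it was 0.273 against 0.269.

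**6. Covariate adjustment with the draw unchanged.** Adjusting for the outcome's own baseline gives a contrast SD of 0.342, 0.310 or 0.258 at ρ = 0.3, 0.5 or 0.7. The stratified change contrast without adjustment gives 0.370, 0.326 or 0.260. Adjustment does as well or better, and for every outcome.

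**The case against.** The strongest reply is that chance imbalance is not bias. The C versus D draw is random, so the imbalance is already part of the sampling error behind the test and interval. The plan openly declares an unpowered pilot. This stands. A reader might infer that the missing stratification makes the comparison invalid; the documents do not support that.

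Three other strong readings also fail.

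- A reader might take the 2% as applying to each outcome. It applies only to baseline CAFPAS. For another outcome's change from baseline, the variance reduction is at most about 5% when its correlation with CAFPAS is 0.5 (pre-post correlation 0.5 assumed).
- A reader might expect the gain to reach all Aim 2 analyses. The within-subject part runs from end of fall, where stratifying on study baseline does little or nothing.
- A reader might suppose that Hypothesis 2a rests on C versus D alone. Its first part compares kits with recipes, which the same students receive in turn, and Groups A and B also bear on support versus none.

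It can also be said that the text does not state outright that controls finish baseline before the draw. That is correct: the Control Condition paragraph mentions access only. Completion is a firm inference from the eligibility tasks under Procedures, from Subject Selection and from the exclusion rule.

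Finally, covariate adjustment alone recovers most of what stratification offers. This also stands, and it is why the remedy includes adjustment. It does not answer the point, because the plan has neither.

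**Conclusion.** The concern holds as a point of precision and interpretability, of modest weight. The assignment text contradicts itself for controls. A baseline gap above 0.5 SD on any one measure has about a one-in-six chance in either direction, and no baseline adjustment is planned.

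The one-in-six figure needs only 16 per group and approximate normality. The precision gains rest on assumed correlations, because the plan gives none. The between-subjects comparisons planned for Aim 2 stand to gain.

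**What to change.** 1. **Allocation of controls.** Limit the availability sentence to the class periods. For controls, state that one draw is made once all control baselines are complete: controls are split at the median baseline CAFPAS score, and half of each stratum is randomised to Group C and half to Group D. Include the stratum in the C versus D models.
2. **Analysis.** In the support versus no support comparison of each outcome, adjust for that outcome's own pre-support value. State in advance which visit supplies it.

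**Cost.** One protocol sentence and the added model terms. The draw must wait for all control baselines; kits start in mid-January 2020 and baseline closes before the October 2019 classes, so there is time in the schedule. Because the data-handling section lets only the biostatistics staff view raw data, they would have to supply the CAFPAS split.

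This copy carries an approval stamp of 14 April 2020, so the draw may already have been made. The second change then remains available if it is written down before analysis, and the first can be carried into the larger study.
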